4.3 TREATMENT COMPLIANCE

Compliance will be assured by administration of all trial medication in the study centre under supervision of the investigating physician or a designee. The measured plasma concentrations and/or urinary excretion will provide additional confirmation of compliance.

Subjects who are non-compliant (for instance, who do not appear for scheduled visits or violate trial restrictions) may be removed from the trial and the CRF will be completed accordingly (for further procedures, please see Section [3.3.4.1](#)).

5. VARIABLES AND THEIR ASSESSMENT

5.1 EFFICACY - CLINICAL PHARMACOLOGY

5.1.1 Endpoints of efficacy

No efficacy endpoints will be evaluated in this trial.

5.1.2 Assessment of efficacy

Not applicable.

5.2 SAFETY

5.2.1 Endpoints of safety

Primary endpoint to assess safety and tolerability of BI 730357 is the number [N (%)] of subjects with adverse reactions.

5.2.2 Assessment of adverse events

5.2.2.1 Definitions of adverse events

Adverse event

An adverse event (AE) is defined as any untoward medical occurrence in a patient or clinical investigation subject administered a medicinal product and which does not necessarily have to have a causal relationship with this treatment.

An AE can therefore be any unfavourable and unintended sign (including an abnormal laboratory finding), symptom, or disease temporally associated with the use of a medicinal product, whether or not considered related to the medicinal product.

Adverse reaction

An adverse reaction is defined as a response to a medicinal product which is noxious and unintended. Response in this context means that a causal relationship between a medicinal product and an adverse event is at least a reasonable possibility. Adverse reactions may arise from use of the product within or outside the terms of the marketing authorisation or from occupational exposure. Conditions of use outside the marketing authorization include off-label use, overdose, misuse, abuse and medication errors.

Serious adverse event

A serious adverse event (SAE) is defined as any AE which:

- results in death,
- is life-threatening, this refers to an event in which the patient was at risk of death at the time of the event; it does not refer to an event that hypothetically might have caused death if more severe,
- requires inpatient hospitalisation or prolongation of existing hospitalisation,
- results in persistent or significant disability or incapacity,
- is a congenital anomaly/birth defect,
or
- is to be deemed serious for any other reason if it is an important medical event when based upon appropriate medical judgment which may jeopardise the patient and may require medical or surgical intervention to prevent one of the other outcomes listed in the above definitions.

Medical and scientific judgement should be exercised in deciding whether other situations should be considered serious reactions, such as important medical events that might not be immediately life threatening or result in death or hospitalisation but might jeopardise the patient or might require intervention to prevent one of the other outcomes listed above.

Examples of such events are intensive treatment in an emergency room or at home for allergic bronchospasm, blood dyscrasias or convulsions that do not result in hospitalisation or development of dependency or abuse. Any suspected transmission via a medicinal product of an infectious agent is also considered a serious adverse reaction.

AEs considered 'Always Serious'

In accordance with the European Medicines Agency initiative on Important Medical Events, Boehringer Ingelheim has set up a list of further AEs, which by their nature, can always be considered to be 'serious' even though they may not have met the criteria of an SAE as given above.

The latest list of 'Always Serious AEs' can be found in the RDC system, a remote data capture system which allows the entry of trial data at the trial site. These events should always be reported as SAEs as described above.

Cancers of new histology and exacerbations of existing cancer must be reported as a serious event regardless of the duration between discontinuation of the drug and the occurrence of the cancer.

Adverse events of special interest (AESIs)

The term AESI relates to any specific AE that has been identified at the project level as being of particular concern for prospective safety monitoring and safety assessment within this trial, e.g. the potential for AEs based on knowledge from other compounds in the same class. AESI need to be reported to the Sponsor's Pharmacovigilance Department within the same timeframe that applies to SAE, please see above.

Proprietary confidential information © 2017 Boehringer Ingelheim International GmbH or one or more of its affiliated companies

The following are considered as AESIs in this trial:

- Hepatic injury, as defined by the following alterations of hepatic laboratory parameters:
 - an elevation of AST and/or ALT ≥ 3 -fold ULN combined with an elevation of total bilirubin ≥ 2 -fold ULN measured in the same blood sample, and/or
 - marked peak aminotransferase (ALT, and/or AST) elevations ≥ 10 fold ULN

These lab findings constitute a hepatic injury alert and the patients showing these lab abnormalities need to be followed up according to the 'DILI checklist' provided in the ISF. In case of clinical symptoms of hepatic injury (icterus, unexplained encephalopathy, unexplained coagulopathy, right upper quadrant abdominal pain, etc.) without lab results (ALT, AST, total bilirubin) available, the Investigator should make sure these parameters are analysed, if necessary in an unscheduled blood test. Should the results meet the criteria of hepatic injury alert, the procedures described in the DILI checklist should be followed.

Intensity of AEs

The intensity of the AE should be judged based on the following:

Mild: Awareness of sign(s) or symptom(s) that is/are easily tolerated
Moderate: Enough discomfort to cause interference with usual activity
Severe: Incapacitating or causing inability to work or to perform usual activities

Causal relationship of AEs

The definition of an adverse reaction implies at least a reasonable possibility of a causal relationship between a suspected medicinal product and an adverse event. An adverse reaction, in contrast to an adverse event, is characterised by the fact that a causal relationship between a medicinal product and an occurrence is suspected.

Medical judgment should be used to determine the relationship, considering all relevant factors, including pattern of reaction, temporal relationship, de-challenge or re-challenge, confounding factors such as concomitant medication, concomitant diseases and relevant history.

Arguments that may suggest that there is a reasonable possibility of a causal relationship could be:

- The event is consistent with the known pharmacology of the drug
- The event is known to be caused by or attributed to the drug class.
- A plausible time to onset of the event relative to the time of drug exposure.
- Evidence that the event is reproducible when the drug is re-introduced
- No medically sound alternative aetiologies that could explain the event (e.g. pre-existing or concomitant diseases, or co-medications).
- The event is typically drug-related and infrequent in the general population not exposed to drugs (e.g. Stevens-Johnson syndrome).

Proprietary confidential information © 2017 Boehringer Ingelheim International GmbH or one or more of its affiliated companies

- An indication of dose-response (i.e. greater effect size if the dose is increased, smaller effect size if dose is diminished).

Arguments that may suggest that there is no reasonable possibility of a causal relationship could be:

- No plausible time to onset of the event relative to the time of drug exposure is evident (e.g. pre-treatment cases, diagnosis of cancer or chronic disease within days / weeks of drug administration; an allergic reaction weeks after discontinuation of the drug concerned)
- Continuation of the event despite the withdrawal of the medication, taking into account the pharmacological properties of the compound (e.g. after 5 half-lives). Of note, this criterion may not be applicable to events whose time course is prolonged despite removing the original trigger.
- Additional arguments amongst those stated before, like alternative explanation (e.g. situations where other drugs or underlying diseases appear to provide a more likely explanation for the observed event than the drug concerned).
- Disappearance of the event even though the study drug treatment continues or remains unchanged.

5.2.2.2 Adverse event collection and reporting

AEs collection

Upon enrolment into a trial, the subject's baseline condition is assessed (for instance, by documentation of medical history/concomitant diagnoses), and relevant changes from baseline are noted subsequently.

Subjects will be required to report spontaneously any AEs as well as the time of onset, end, and intensity of these events. In addition, each subject will be regularly assessed by the medical staff throughout the clinical trial and whenever the Investigator deems necessary. As a minimum, subjects will be questioned for AEs (and concomitant therapies) at the time points indicated in the [Flow Chart](#). Assessment will be made using non-specific questions such as 'How do you feel?'. Specific questions will be asked wherever necessary in order to more precisely describe an AE.

A careful written record of all AEs shall be kept by the Investigator in charge of the trial. Records of AEs shall include data on the time of onset, end time, and intensity of the event as well as any treatment or action required for the event and its outcome.

[figure not shown]
The following must be collected and documented on the appropriate CRF(s) by the Investigator:

- From signing the informed consent onwards through the residual effect period (REP), until an individual subject's end of trial:
 - All AEs (serious and non-serious) and all AESIs.
 - The only exception to this rule are AEs (serious and non-serious) and AESIs in Phase I trials in healthy volunteers, when subjects discontinue from the trial due to screening failures prior to administration of any trial medication. In

Proprietary confidential information © 2017 Boehringer Ingelheim International GmbH or one or more of its affiliated companies

these cases, the subjects' data must be collected at trial site but will not be entered in the CRF or trial database and will not be reported in the CTR.

- After the individual subject's end of trial:
 - The Investigator does not need to actively monitor the subject for AEs but should only report relevant SAEs and relevant AESIs of which [REDACTED] may become aware of.

The REP for BI 730357, when measurable drug levels or PD effects are still likely to be present after the last administration, is not known for this first-in-human trial. Therefore, all AEs reported until the end of trial examination (last per protocol contact) will be considered on treatment; please see Section [7.3.3](#).

AE reporting to Sponsor and timelines

The Investigator must report SAEs, AESIs, and non-serious AEs which are relevant for the reported SAE or AESI, on the BI SAE form via fax immediately (within 24 hours of awareness) to the Sponsor's unique entry point (country specific contact details will be provided in the ISF). The same timeline applies if follow-up information becomes available. In specific occasions the Investigator could inform the Sponsor upfront via telephone. This does not replace the requirement to complete and fax the BI SAE form.

With receipt of any further information to these events, a follow-up SAE form has to be provided. For follow-up information the same rules and timeline apply as for initial information.

Information required

For each AE, the Investigator should provide the information requested on the appropriate CRF pages and the BI SAE form (if applicable). The Investigator should determine the causal relationship to the trial medication.

The following should also be recorded as an (S)AE in the CRF and on the SAE form (if applicable):

- Worsening of the underlying disease or of other pre-existing conditions
- Changes in vital signs, ECG, physical examination and laboratory test results, if they are judged clinically relevant by the Investigator.

If such abnormalities already pre-exist prior trial inclusion they will be considered as baseline conditions.

All (S)AEs, including those persisting after individual subject's end of trial must be followed up until they have resolved, have been sufficiently characterised, or no further information can be obtained.

5.2.3 Assessment of safety laboratory parameters

For the assessment of laboratory parameters, blood and urine samples will be collected by the trial site at the time points indicated in the [Flow Chart](#) after the subjects have fasted for at least 10 h (excluding 6-hour post-dose sample). Overnight fasting is not required at the discretion of the Investigator or designee for retests.

The parameters that will be determined are listed in Tables 5.2.3: 1 and [5.2.3: 2](#). Reference ranges will be provided in the ISF, Section 10.

Table 5.2.3: 1 Routine laboratory tests

Functional lab group	Test name	A ¹	B ²	C ³	D ⁴	E ⁵
Haematology	Haematocrit	X	X	X	X	X
	Haemoglobin	X	X	X	X	X
	Red blood cells (RBC)	X	X	X	X	X
	White blood cells (WBC)	X	X	X	X	X
	Platelets	X	X	X	X	X
	Reticulocyte count	X	X	X	X	X
Automatic WBC differential (relative and absolute)	Neutrophils	X	X	X	X	X
	Eosinophils	X	X	X	X	X
	Basophils	X	X	X	X	X
	Monocytes	X	X	X	X	X
	Lymphocytes	X	X	X	X	X
		X		X		
Manual differential WBC (if automatic differential WBC is abnormal)	Polymorphnuclear neutrophils (segs), band neutrophils (stabs), eosinophils, basophils, monocytes, lymphocytes					
Coagulation	Activated partial thromboplastin time (aPTT) Prothrombin Time (Quick and INR)	X	X	X	--	X
		X	X	X	--	X

¹ A: parameters to be determined at visit 1 (screening examination)

²B: parameters to be determined at visit 2-4 on Days -3 to -1 (for time point, refer to Flow Chart)

3 C: parameters to be determined at visits 2-4 on Days 1 to 4 (for time points, refer to Flow Chart)

⁴ D: parameters to be determined at visits 2–4 on Day 8 (for time point, refer to Flow Chart)

⁵ E: parameters to be determined at visit 5 (end of trial examination)

Proprietary confidential information © 2017 Boehringer Ingelheim International GmbH or one or more of its affiliated companies

Table 5.2.3: 1 Routine laboratory tests (cont.)

Functional lab group	Test name	A ¹	B ²	C ³	D ⁴	E ⁵
Enzymes	Aspartate aminotransferase (AST/GOT)	X	X	X	--	X
	Alanine aminotransferase (ALT/GPT)	X	X	X	--	X
	Alkaline phosphatase (AP)	X	X	X	--	X
	Gammaglutamyl transferase (GGT)	X	X	X	--	X
	Lactate dehydrogenase	X	X	X	--	X
	Lipase	X	--	--	--	X
Substrates	Plasma glucose	X	X	X	--	X
	Creatinine	X	X	X	--	X
	Total bilirubin	X	X	X	--	X
	Direct bilirubin	X	X	X	--	X
	Total protein	X	X	X	--	X
	C-Reactive Protein (CRP)	X	X	X	--	X
	Urea in serum	X	X	X	--	X
	Phosphate in serum	X	X	X	--	X
	Total cholesterol	X	X	X	--	X
*Electrolytes	Triglycerides	X	--	--	--	X
	Calcium	X	X	X	--	X
	Sodium	X	X	X	--	X
Hormones	Potassium	X	X	X	--	X
	Thyroid stimulating hormone (TSH)	X	--	--	--	--
Urinalysis (Stix)	Urine nitrite	X	X	X	--	X
	Urine protein	X	X	X	--	X
	Urine glucose	X	X	X	--	X
	Urine ketone	X	X	X	--	X
	Urobilinogen	X	X	X	--	X
	Urine bilirubin	X	X	X	--	X
	Urine RBC	X	X	X	--	X
	Urine WBC	X	X	X	--	X
	Urine pH	X	X	X	--	X
Urine sediment (microscopic examination if erythrocytes, leukocytes nitrite or protein are abnormal in urine)	Only positive findings will be reported (e.g. presence of sediment bacteria, casts in sediment, squamous epithelial cells, erythrocytes, leukocytes)				--	

¹ A: parameters to be determined at visit 1 (screening examination)² B: parameters to be determined at visits 2-4 on Days -3 to -1 (for time point, refer to [Flow Chart](#))³ C: parameters to be determined at visits 2-4 on Days 1 to 4 (for time points, refer to Flow Chart)⁴ D: parameters to be determined at visits 2-4 on Day 8 (for time point, refer to Flow Chart)⁵ E: parameters to be determined at visit 5 (end of trial examination)

Manual differential white blood cell count or urine sediment examinations will only be performed if there is an abnormality in the automatic blood cell count or in the urinalysis, respectively.

The tests listed in Table [5.2.3: 2](#) are exclusionary laboratory tests which may be repeated as required. The results will not be entered in the CRF/database and will not be reported in the

Proprietary confidential information © 2017 Boehringer Ingelheim International GmbH or one or more of its affiliated companies

CTR. Except for drug screening, it is planned to perform these tests during screening only. Drug screening will be performed at screening and prior to each administration of trial medication on Day 1 (for time points refer to [Flow Chart](#)).

Table 5.2.3: 2 Exclusionary laboratory tests

Functional lab group	Test name
Drug screening (urine)	Amphetamine/MDA Barbiturates Benzodiazepine Cannabis Cocaine Methadone Methamphetamines/MDMA/XTC Opiates Phencyclidine Tricyclic antidepressants
Infectious serology (blood)	Hepatitis B surface antigen (qualitative) Hepatitis B core antibody (qualitative) Hepatitis C antibodies (qualitative) HIV-1 and HIV-2 antibody (qualitative)

To encourage compliance with alcoholic restrictions, a breath alcohol test (Alcotest® 7410, Dräger AG, Lübeck, Germany) will be performed prior to each treatment at time points indicated in the Flow Chart, and may be repeated at any time during the study at the discretion of an Investigator or designee. The results will not be included in the CTR.

The laboratory tests listed in Table 5.2.3: 1 and 5.2.3: 2 will be performed at [REDACTED] [REDACTED] with the exception of the drug screening tests. These tests will be performed at the trial site using e.g. MAHSAN® -Kombi/DOA10 rapid test.

Laboratory data will be transmitted electronically from the laboratory to the trial site.

5.2.4 Electrocardiogram

5.2.4.1 12-lead resting ECG

Twelve-lead resting ECGs (I, II, III, aVR, aVL, aVF, V1 - V6) will be recorded using a computerised electrocardiograph (CardioSoft EKG System, GE Medical Systems, Freiburg, Germany) at the time points given in the Flow Chart.

In order to achieve a stable heart rate at rest and to assure high quality recordings at comparable resting phases, all ECGs will be recorded for a 10-sec duration after the subjects have rested for at least 5 min in a supine position. The site personnel will be instructed to assure a relaxed and quiet environment so that all subjects are at complete rest during the recordings. ECG assessment will always precede all other study procedures of the same time point (except blood drawing from an intravenous cannula which is already in place) to avoid impact of sampling on the ECG quality.

Proprietary confidential information © 2017 Boehringer Ingelheim International GmbH or one or more of its affiliated companies

All ECGs will be stored electronically on the Muse CV Cardiology System (GE Medical Systems, Freiburg, Germany). Electrode placement will be performed according to the method of Wilson, Goldberger and Einthoven modified by Mason and Likar (hips and shoulders instead of ankles and wrists). Precise electrode placement will be marked with an indelible mark on the skin to allow reproducible placement throughout the study.

ECGs will be recorded as single ECGs or as triple ECGs (three single ECGs recorded within 180 sec) as indicated in the [Flow Chart](#).

All locally printed ECGs will be evaluated by the Investigator or a designee.

ECGs may be repeated for quality reasons (like alternating current artefacts, muscle movements, electrode dislocation). For time points with triple ECGs, all three single ECGs will be repeated. For the repeats due to quality reasons, only the repeated ECG recordings will be sent to the central ECG lab, whereas the initially recorded ECGs will be discarded.

Additional (unscheduled) ECGs may be collected by the Investigator for safety reasons. These ECGs are assigned to the prior scheduled time point. Unscheduled ECGs will not be included into the statistical analysis of interval lengths.

For the inclusion or exclusion (see Section [3.3](#)) of a subject and for the assessment of cardiac safety during the study, the QT and QTcB values generated by the ECG machines or their manual corrections by the Investigators will be used. In doubtful cases, ECGs may be sent upfront for centralised evaluation (see below). In this case, these centrally measured results would overrule any other results obtained.

Abnormal findings will be reported as AEs (during the trial) or baseline conditions (at screening) if judged clinically relevant by the Investigator. Any ECG abnormalities will be monitored carefully and, if necessary, the subject will be removed from the trial and will receive the appropriate medical treatment.

[REDACTED]

For blinding arrangements see Section [4.1.5](#).

Proprietary confidential information © 2017 Boehringer Ingelheim International GmbH or one or more of its affiliated companies

Assessed ECGs will comply with the ICH E14 guidance document and supplements [[R05-2311](#), [R13-0801](#), [R13-4095](#)] as well as the FDA requirements for annotated digital ECGs [[R09-4830](#)].

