Statistical methods: Descriptive statistics will be calculated for all endpoints. SRD part : Dose proportionality will be explored under fasted conditions using a regression model. A 95% confidence interval for the slope will be computed. BA part : Relative bioavailability will be estimated by the ratios of the geometric means (tablet / PfOS, tablet fed / tablet fasted) for the secondary endpoints. Additionally, their two-sided 90% confidence intervals (CIs) will be provided. Since the main focus is on estimation and not testing, an acceptance range was not specified. The statistical model will be an ANOVA on the logarithmic scale including effects for 'sequence', 'subjects nested within sequences', 'period' and 'treatment'. CIs will be calculated based on the residual error from ANOVA.				

FLOW CHART FOR THE SINGLE RISING DOSE PART

Visit	Day	Planned time (relative to drug administration [h:min])	Approximate clock time of actual day [h:min]	Event and comment	Safety laboratory	PK blood ^{10, 11}	PK urine ^{10, 12}	Blood sampling for biomarkers ^{10, 13}	12-lead ECG	Continuous ECG monitoring	Vital signs (BP, PR)	Questioning for AEs and concomitant therapy ⁶
1	-21 to -1			Screening (SCR) ¹	x				x ¹⁴		x	
2/3*	-3 to -1	-72:00 ⁷	08:00	Ambulatory visit	x							x
	1	-2:00	06:00	Admission to trial site in visits 2-3, allocation to treatment ² in visit 2 only	x ^{2,5}	x ²	x ²	x ²	x ^{2,9}	x ²	x ²	
		-0:30	07:30	Standard breakfast in dose groups 8-10 ¹⁶								
		0:00	08:00	Drug administration			▲			▲		
		0:30	08:30		x			x ⁹		x	x	
		1:00	09:00		x			x ⁹		x	x	
		1:30	09:30		x							
		2:00	10:00	240 mL fluid intake	x			x	x ⁹		x	x
		2:30	10:30		x							
		3:00	11:00		x			x ⁹		x	x	
		4:00	12:00	240 mL fluid intake, thereafter lunch ³	x ⁸	+	x	x ⁹		x	x	
		5:00	13:00		x			x ⁹		x	x	
		6:00	14:00		x	x		x	x ⁹	▼	x	x
		8:00	16:00	Snack (voluntary) ³	x	+		x ⁹		x	x	
		10:00	18:00	Dinner ³	x			x ⁹		x	x	
		12:00	20:00		x	+		x ⁹		x	x	
	2	24:00	08:00	Breakfast (voluntary) ³ , discharge from trial site	x	x	+	x	x ⁹		x	x
		34:00	18:00	Ambulatory visit	x			x ⁹		x	x	
	3	48:00	08:00	Ambulatory visit	x		▼	x	x ⁹		x	x
	4	72:00	08:00	Ambulatory visit	x	x					x	x
	5	96:00	08:00	Ambulatory visit	x			x			x	x
	8	168:00	08:00	Ambulatory visit	x ¹⁵	x		x				x
5	9 to 13			End of trial (EOT) examination ⁴	x				x ¹⁴		x	x

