- Careful dose selection as described in Section 2.1. In addition, dose escalation will be shallow and both, starting dose [REDACTED] [REDACTED] [REDACTED] [REDACTED] have ample safety margins with respect to the preclinical findings. Finally, dose selection was based on a sound preclinical package including 4 week toxicological studies (not only 2 weeks).
- Preliminary measurement of BI 730357 plasma concentrations and preliminary determination of PK parameters (C_{max} , AUC_{0-24} see Section 7.3.4). [REDACTED]
[REDACTED] Further dose progression would only be allowed after a safety interim analysis and filing and approval of a substantial CTP amendment.
- An extensive safety laboratory will be performed with special focus on full blood exam (see [Flow Chart](#)).

Proprietary confidential information © 2017 Boehringer Ingelheim International GmbH or one or more of its affiliated companies

- For safety reasons, during the single rising dose part each dose group of 8 subjects (6 on active, 2 on placebo) will be divided into two cohorts of 4 subjects each (3 on active, 1 on placebo). These two cohorts will be separated by at least 48 hours (between 1st subject of each cohort),
[REDACTED]
[REDACTED]. The first cohort will be dosed in a single blinded, fixed sequence fashion (active - placebo - active - active) and the drug administration will be separated by at least 60 min between the first 3 subjects. This design ensures that between first and second active dose of each dose level there is a time interval of at least 2 hours, which is expected to be sufficient to detect relevant acute effects of BI 730357. If BI 730357 was safe and well tolerated during these initial administrations, the remaining subjects of the respective dose level could be dosed as close as 10 minutes apart.
- A thorough ECG monitoring including continuous ECG measurement over 6 hours post dose to cover the anticipated period of highest drug exposure and additional repeated single 12-lead ECGs over 48 hours following drug administration. Dose escalation would be stopped as soon as at least 2 subjects at one dose level showed relevant QT prolongation (see Section [3.3.4.2](#) for details).
- The subjects will stay at the trial site (BI Human Pharmacology Centre) for at least 24 hours after study drug administration at each dose level.
[REDACTED]
[REDACTED]

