3.3.4.2 Discontinuation of the trial by the Sponsor

Boehringer Ingelheim reserves the right to discontinue the trial overall or at a particular trial site at any time for any of the following reasons:

1. New toxicological findings or serious adverse events invalidate the earlier positive benefit-risk-assessment. More specifically, the trial will be terminated if more than 50% of the subjects show drug-related and clinically relevant adverse events of moderate or severe intensity, or if at least one drug-related serious adverse event is reported
2. The expected enrolment goals overall or at a particular trial site are not met
3. Violation of GCP, or the CTP by a trial site or Investigator, disturbing the appropriate conduct of the trial
4. The Sponsor decides to discontinue the further development of the investigational product
5. Dose escalation will be stopped as soon as at least 2 subjects at one dose level on active drug showed relevant individual QT prolongation, i.e. a QTc increase of greater 60 ms from baseline in connection with absolute QT or QTc greater than 500 ms, which has been confirmed by a repeat ECG recording
6. Dose escalation will be stopped based on preliminary PK results (plasma) as soon as measured (in at least one subject) or estimated C_{max} / AUC_{0-24} of BI 730357 exceed [REDACTED] (upper limit of acceptable exposure in this trial, see Section 2.1).

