The trial medication will be administered to the subjects, while in a sitting or standing position, as an oral dose together with about 240 mL of water under supervision of the investigating physician or an authorised designee in the morning of Day 1. The so-called four-eye principle (two-person rule) should be applied for administration of trial medication and – if applicable – its preparation (e.g. reconstitution), if correct dosage cannot be ensured otherwise. Administration will be performed following an overnight fast, which is to start no later than 10 h before the scheduled dosing.

In treatment T2 (tablet fed) of the BA part and dose groups 9 (400 mg BI 730357 or placebo) and 10 (800 mg BI 730357 or placebo) of the SRD part, a high-fat, high-calorie breakfast will be served 30 min before drug administration. In dose group 8 (400 mg BI 730357 or placebo) of the SRD part, a standard continental (normal-fat, normal-calorie) breakfast will be served 30 min before drug administration. The test meals must be completely consumed prior to drug administration. The composition of the standard high-fat, high-calorie breakfast will be in compliance with the FDA guidance ‘Food-Effect Bioavailability and Fed Bioequivalence Studies’ [[R03-2269](#)] as detailed in Table 4.1.4: 3. The composition of the standard continental breakfast will be detailed in [Table 4.1.4: 4](#).

Table 4.1.4: 3

Composition of the high-fat, high-calorie meal

Ingredients	kcal
Sum ¹	984

¹ The total caloric content was supplied approximately as following: 150 kcal as protein, 250 kcal as carbohydrate, and 500 to 600 kcal as fat.

Table 4.1.4: 4

Composition of the continental breakfast

Ingredients	kcal
Sum ¹	458

¹ The total caloric content was supplied approximately as following: 88 kcal as protein, 133 kcal as carbohydrate, and 237 kcal as fat.

Subjects will be kept under close medical surveillance until at least 24 h following drug administration. During the first 6 hours after drug administration subjects of the SRD part will be confined to bed with a bed inclination angle of at least 45 degrees unless lower or supine positioning is required for trial-related measurements (e.g. recording of 12-lead ECG). During the first 4 hours after drug administration subjects of the BA part will only be allowed to lie down if supine positioning is required for trial-related measurements (e.g. recording of 12-lead ECG). For restrictions with regard to diet see Section [4.2.2.2](#).

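### QTcB is the only heart-rate correction the visible protocol names for on-study cardiac safety, so the QT stopping rule can trigger later than on QTcF when heart rate falls; counting either correction closes the gap without loosening the rule

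*Protocol*

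**What the plan says.** Protocol 2.3 gives the principle: "Dose escalation would be stopped as soon as at least 2 subjects at one dose level showed relevant QT prolongation". Protocol 3.3.4.2, criterion 5, defines that prolongation in an active subject as "a QTc increase of greater 60 ms from baseline in connection with absolute QT or QTc greater than 500 ms". A single tracing is not enough: the finding must be one "which has been confirmed by a repeat ECG recording". The increase and the absolute condition must both be met. Criterion 5 does not say which correction QTc means, and the protocol's abbreviation list allows either Fridericia or Bazett.

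The one visible sentence that fixes the values for on-study cardiac safety is in Protocol 5.2.4.1: "the QT and QTcB values generated by the ECG machines or their manual corrections by the Investigators will be used". The same section allows ECGs to be sent ahead for central evaluation in doubtful cases, and then "these centrally measured results would overrule any other results obtained". The text that describes the central evaluation is blacked out.

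On timing, the Flow Chart for the single rising dose part puts the pre-dose ECG at -2:00, on the row "Admission to trial site in visits 2-3". At -0:30 there is "Standard breakfast in dose groups 8-10". Protocol 4.1.4 adds: "During the first 6 hours after drug administration subjects of the SRD part will be confined to bed".

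**The concern.** The two corrections differ by a factor that depends only on heart rate. If the rate is lower after dosing than at baseline, the same repolarisation change gives a smaller increase on QTcB than on QTcF. Raw QT above 500 ms does not help, because it serves only the absolute condition, and the QTc increase above 60 ms is required as well.

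The schedule leaves room for the rate to move between baseline and the post-dose ECGs. Baseline is taken around admission and the ECGs from 0:30 to 6:00 are taken during bed confinement, while dose groups 8 to 10 also eat in between. The documents do not say which way the rate moves or by how much.

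Criterion 5 is the pre-specified QT gate. By version 4.0 the fasted groups up to 400 mg had been dosed (Protocol 11, rationale for amendment 3), so the planned increase still ahead is from 400 to 800 mg fed. At stake is whether a subject with a confirmed QTcF rise above 60 ms and raw QT above 500 ms counts towards the two.

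**Working it through.** The plan states no operating characteristic for criterion 5, so there is no figure of its own to reproduce.

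**Inputs from the documents.** The 60 ms and 500 ms limits, the raw-QT alternative and the two-subject count (Protocol 3.3.4.2); six active subjects per group (3.2); pulse 50 to 90 bpm at entry (3.3.3).

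**Assumptions.** Baseline QTcF of 410, 420 or 430 ms, and all heart-rate changes. The documents give neither.

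**Formulas.** With RR = 60/HR:
- QTcB = QTcF × f, where f = (HR/60)^(1/6): 0.9856 at 55 bpm, 1.0134 at 65, 1.0491 at 80.
- QT = QTcF × g, where g = (60/HR)^(1/3): 1.0294 at 55 bpm.
- Rule: increase > 60 ms AND (QT > 500 ms OR QTc > 500 ms).

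**Which condition causes the gap.** Above 60 bpm QTcB exceeds QTcF; below 60 bpm raw QT exceeds QTcF. The absolute condition is therefore never harder to meet with QTcB than with QTcF. The gap lies only in the increase condition.

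**Worked case.** HR 65 to 55 bpm, QTcF 430 to 502 ms:
- QTcF increase: 502 − 430 = 72 ms, above 60.
- QTcB: 430 × 1.0134 = 435.8 and 502 × 0.9856 = 494.8; increase 59.0 ms, not above 60.
- Raw QT: 502 × 1.0294 = 517 ms, so the absolute condition is met either way.

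The rule is met on QTcF and not met on QTcB.

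**QTcF rise needed to trigger in one subject.** With baseline QTcF F0, and subscripts 0 and 1 for baseline and post-dose:
- QTcB rule: max[(F0·f0 + 60)/f1 − F0; min(500/f1, 500/g1) − F0]
- QTcF rule: max[60; min(500, 500/g1) − F0]
- Either rule: the smaller of the two

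Entries are QTcB / QTcF / either, in ms:

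| HR (bpm) | F0 = 410 | F0 = 420 | F0 = 430 |
|---|---|---|---|
| 65 to 55 | 75.7 / 75.7 / 75.7 | 72.7 / 65.7 / 65.7 | 73.0 / 60 / 60 |
| 70 to 60 | 90 / 90 / 90 | 80 / 80 / 80 | 71.2 / 70 / 70 |
| 75 to 55 | 82.6 / 75.7 / 75.7 | 83.2 / 65.7 / 65.7 | 83.7 / 60 / 60 |
| 55 to 65 | 83.4 / 90 / 83.4 | 73.4 / 80 / 73.4 | 63.4 / 70 / 63.4 |
| 60 to 70 | 77.3 / 90 / 77.3 | 67.3 / 80 / 67.3 | 57.3 / 70 / 57.3 |
| 55 to 80 | 66.6 / 90 / 66.6 | 56.6 / 80 / 56.6 | 46.6 / 70 / 46.6 |

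For the two 10 bpm falls, QTcB is later by 0 to 13 ms; for 75 to 55 bpm it is later by 7 to 24 ms. For the three rises QTcB is earlier, by 7, 13 and 23 ms. The either rule contains every QTcB trigger, so it is never later than QTcB.

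**Group level, illustration only.** Assume baseline QTcF 405 ms (SD 15), mean QTcF rise 80 ms (SD 15), baseline HR SD 5 bpm, HR-change SD 4 bpm, six independent subjects and no repeat-ECG step. The chance that at least two of six meet the rule on QTcB / QTcF / either is 0.55 / 0.98 / 0.98 for a mean fall from 70 to 50 bpm, 0.70 / 0.70 / 0.79 for 70 to 60, and 0.85 / 0.46 / 0.85 at a steady 70.

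**Heart rate alone.** With no drug effect, take QT = Q60 × (60/HR)^b with b = 0.25, 1/3, 0.40 or 0.50, Q60 from 380 to 450 ms in 5 ms steps, HR 50 to 90 bpm at both times and baseline QTcB at most 450 ms. That gives 18,614 + 20,582 + 22,181 + 24,846 = 86,223 combinations, with no trigger on either correction.

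**The case against.** The strongest reply is that a missed trigger presumes QTcF is the truer value. The documents hold no QT-RR data. If the true exponent were 0.50, the rate fall alone would add 430 × ((65/55)^(1/6) − 1) = 12 ms to the QTcF rise in the worked case, and QTcB would be right to say the rule is not met. That stands: the calculation shows two formulas disagreeing, not one failing.

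A reader might also infer that the rule rests on machine Bazett values alone. The text does not go that far. It also names raw QT and the Investigators' manual corrections, and a central reading can overrule. The link from 5.2.4.1 to criterion 5 is itself an inference, though the natural one. What remains is that raw QT cannot satisfy the increase condition, manual corrections of QT and QTcB are not a different rate correction, and central reading is optional and its correction is not visible.

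Third, the practical effect is small. QTcB usually triggers earlier at steady or rising rate, and some falls give no delay. Several safeguards surround the rule: five minutes' supine rest, Investigator review of printed ECGs, a documented Safety Review before each escalation, and the instruction to stop on safety concerns (Protocol 5.2.4.1 and 3.1). The worked case misses by about 1 ms and would probably be treated as doubtful. This also stands, and it keeps the point minor. But these safeguards rest on judgement, in a case where the written rule would read as not met.

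**Conclusion.** The point holds as an inexpensive clarification with a modest safety gain. On the visible text the increase condition is judged on QTcB unless a discretionary central reading overrules, so a fall in heart rate can delay the trigger relative to QTcF. The size rests on the assumed heart-rate changes and baseline QTcF, and on applying 5.2.4.1 to criterion 5. A changed escalation decision would be uncommon: it needs a large QTcF rise and a sizeable rate fall, confirmed on repeat, in enough active subjects to alter the count of two.

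Two stronger readings are not supported. One is that QTcF should replace QTcB: that would loosen the rule by 7, 13 and 23 ms in the three rate rises checked. The other is that heart rate alone could stop the trial, which did not happen anywhere in the range checked. Nothing is claimed about the blacked-out central evaluation.

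**What to change.** In Protocol 5.2.4.1, add QTcF, derived from the same QT and RR, to the values used for on-study cardiac safety. In criterion 5, state that a subject counts if the rule is met on QTcB or on QTcF, each taken against its own baseline. Leave the 60 and 500 ms limits, the raw-QT alternative, the repeat ECG and the two-subject count as they are.

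Leave central reading discretionary and overruling, as now, and add that any such reading reports both corrections and is judged by the same either rule. Do not make it compulsory whenever the corrections disagree. Take HR 55 to 80 bpm and QTcF 430 to 480 ms: QTcB goes from 423.8 to 503.6, an increase of 79.8 ms, and the subject counts today; QTcF rises only 50 ms. A compulsory reading that reported QTcF alone would remove that subject, and the rule would have been loosened.

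The cost is one sentence in 5.2.4.1, a short addition to criterion 5 and one derived value. No extra ECGs or subjects are needed, since QTcF = QT^(1/3) × QTcB^(2/3). The downside is a few more alerts when the rate falls, some of them rate artefact.
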